1.1. List of Abbreviations

10. *Journal of the American Statistical Association*, 1952, 47, 365-386.

1. *What is the primary purpose of the study?* (e.g., to evaluate the effectiveness of a new treatment, to describe a population, to compare two groups).

10. *Journal of the American Statistical Association*, 1980, 75, 338-342.

10.1002/anie.201907002

10.1002/anie.201907002

10.1007/s00339-006-0182-0

Digitized by [contact]

Digitized by [contact]

Digitized by [contact]

11. *What is the primary purpose of the following sentence?*

1. **What is the primary purpose of the study?** (1 point)

11. **What is the primary purpose of the `get` method in the `HttpURLConnection` class?**

[REDACTED]	[REDACTED]
[REDACTED]	[REDACTED]

[REDACTED]

2. Document Information

2.1. Purpose and Scope

The purpose of the trial is to evaluate the performance, comfort and ease of use of the [REDACTED] [REDACTED] mask in the home environment.

2.4. Monitoring Arrangements

[REDACTED]

[REDACTED]
[REDACTED]
[REDACTED]
[REDACTED]

[REDACTED]	[REDACTED]
[REDACTED]	[REDACTED]

[REDACTED]
[REDACTED]

2.5. Data Management

[REDACTED]

[REDACTED]

[REDACTED]

[REDACTED]

[REDACTED]

[REDACTED]

[REDACTED]

3. Investigator Information

5.1. Identification of the Medical Device

[REDACTED]

5.2. Device Risk Analysis and Management

6. Justification for a Clinical Trial

6.1. Synopsis

The investigation is a prospective, non-randomized, non-blinded, study. The investigation is designed to evaluate the performance, comfort and ease of use

This study will be conducted in accordance with ICH/GCP guidelines. No deviation from the protocol will be implanted without prior review and approval of the sponsor except where it may be necessary to eliminate an immediate hazard to a research participant. In such case, the deviation will be reported to the sponsor as soon as possible. In this trial the sponsor and the investigator are the same company however the Sponsor will not be the investigator. To ensure roles are clearly defined and kept independent there will be a delegation of authority log to clearly define each individuals tasks.

6.2. Literature Review

[REDACTED]	[REDACTED]
[REDACTED]	[REDACTED]

6.3. Preclinical Testing

[REDACTED]

[REDACTED]

[REDACTED]

[REDACTED]

6.4. Previous Clinical Experience

[REDACTED]

[REDACTED]

[REDACTED]

[REDACTED]

[REDACTED]

[REDACTED]

6.5. Justification for Administration

[REDACTED]

[REDACTED]

[REDACTED]

7. Objectives of the Clinical Investigation

7.1. Hypothesis

[REDACTED]

7.2. Objectives

[figure not shown]
Primary objective:

- To evaluate the performance, comfort and ease of use of the [REDACTED] mask [REDACTED] in a home environment in regards to the participants' view of overall comfort, experience and satisfaction.
- [REDACTED]
- [REDACTED]

7.3. Population

Approximately 60-70 participants will be recruited for the trial by NTLSC.

After identification, the co-ordinating investigator or contact persons from the institutions (or those identified by delegation log) will contact potential participants and obtain informed consent from the subjects to be enrolled.

7.5. Essential Requirements of the Relevant Directive

8. Clinical Investigation Design

8.1. Type of Investigation

This is an open-label (investigators and participants are un-blinded and informed of intended treatment device) single arm study.

8.2. Controls

No control group will be used in this study.

8.3. Bias

The F&P mask is non-blinded and distinguishable. Since the trial mask is the same for the entire population, this study is not blinded.

[REDACTED]	[REDACTED]
[REDACTED]	[REDACTED]

8.4. End Points

8.4.1. Primary Outcomes

- The F&P mask is comfortable to use for the participant as measured by the custom questionnaires and recorded during the interviews.
- The mask is easy to use, accepted by the participant and provides adequate treatment for OSA during in-home use, measured via participant feedback and PAP data download (if applicable)
- The acceptability of the mask [REDACTED] through interview feedback/ participant questionnaire .

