8.4.2. Secondary Outcomes

- Seal performance as measured by leak measurements/PAP data (if applicable).

[REDACTED]
 [REDACTED]

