8.6. Measurements

8.7. Equipment

8.8. Inclusion / Exclusion criteria

Inclusion Criteria:

- Adult (22+ years of age)
- Able to give informed consent
- AHI ≥ 5 on diagnostic night
- Either prescribed APAP, CPAP or Bi-level PAP for OSA
- Fluent in spoken and written English

Exclusion Criteria:

[figure not shown]
- Inability to give informed consent
- Participant intolerant to PAP
- Anatomical or physiological conditions making PAP therapy inappropriate
- Current diagnosis of respiratory disease or CO₂ retention
- Pregnant or may think they are pregnant.

[REDACTED]	[REDACTED]
[REDACTED]	[REDACTED]

[figure not shown]

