8.11. Withdrawal Criteria

Participants will be informed that they have the right to withdraw from the study at any time, without prejudice to their medical care, and are not obliged to state their reasons. The participants is informed that they can revert back to their usual therapy during the clinical investigation if they have reason to do so. Additionally the investigator may withdraw a participant at any time for the following reasons:

- Protocol Violation
- Safety concerns
- Serious illness
- Adverse event

[figure not shown]
The reason for participant discontinuation in the study is to be recorded in the CRF and source document.

[figure not shown]

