9.5. Description of the Statistical Design

Since the trial is to inform product development, no statistical design is required.

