9.7. Pass/Fail Criteria

There is no pass/fail criteria for this trial as the primary objective of the trial is to gain feedback.

[REDACTED]	[REDACTED]
[REDACTED]	[REDACTED]

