9.10. Selection Criteria

All participants who consent, and are fitted with a mask that they attempt to sleep on will be included in the analysis. Please see section 8.10 for information on participant flow throughout the trial.

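### Could adequate OSA treatment, part of a primary outcome, end up judged by participant opinion alone when there is no PAP download?

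*Combined protocol and SAP*

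**What the plan says.** Section 8.4.1 lists three primary outcomes. The second covers whether the mask is easy to use, whether participants accept it, and whether it "provides adequate treatment for OSA during in-home use, measured via participant feedback and PAP data download (if applicable". Section 8.4.2 puts the same condition on leak: "Seal performance as measured by leak measurements/PAP data (if applicable".

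The analysis set in section 9.10 is broad: "All participants who consent, and are fitted with a mask that they attempt to sleep on will be included in the analysis". Its next sentence sends the reader to section 8.10 for participant flow. Section 8.8 requires every participant to be a PAP user: "Either prescribed APAP, CPAP or Bi-level PAP for OSA". Section 8.11 tells participants that "they can revert back to their usual therapy during the clinical investigation".

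On statistical purpose, section 9.5 says: "Since the trial is to inform product development, no statistical design is required". Section 9.7 says: "There is no pass/fail criteria for this trial as the primary objective of the trial is to gain feedback". The visible primary objective in section 7.2 is framed around how participants themselves rate comfort, experience and satisfaction.

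**The concern.** Adequate treatment of sleep apnoea is a physiological matter, and a participant's opinion does not measure breathing during sleep. The bullet names three attributes and two sources without pairing them, and only the objective source is conditional. Taken literally, feedback is the sole evidence of adequacy for anyone without a download.

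Two further points add to this. Section 9.10 admits everyone who tried to sleep on the mask, and no visible sentence names a subset for PAP results. Because section 8.11 allows a return to usual therapy while section 9.10 keeps the participant in the analysis, a download might also contain nights off the trial mask.

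If the report then described treatment as adequate across the whole set, a reader could not tell how many participants had objective trial-mask data behind that statement. For a primary outcome, that is worth checking.

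**Working it through.** The plan gives no figure on this point. Its only visible statistical figure is the usability argument for 30 participants in section 9.6, and nothing here depends on it. The check is therefore mainly a reading of the sections against each other.

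**1. What the bullet can mean**

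| Reading | Ease of use, acceptance | Treatment adequacy | What is left open |
|---|---|---|---|
| Both sources serve all three attributes | Feedback, and download where available | Feedback, and download where available | Feedback alone where there is no download; number with downloads |
| Each source serves what it can measure | Feedback | Download | Number with downloads |

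The second reading is natural, because a PAP download cannot show whether a mask is easy to use and a questionnaire cannot record respiratory events. Under it the main problem disappears and only a denominator is unstated.

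**2. Whether the denominator is missing from the plan**

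This cannot be established. Section 9.10 refers to section 8.10, which is redacted. Section 8.5 (variables) and section 8.12 (number of subjects) are redacted, and no text is visible under 8.6 (measurements) or 8.7 (equipment). These are the places where one would expect the PAP variable and the condition on downloads to be defined. Text that is redacted cannot be counted as absent.

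**3. What depends on the bullet**

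Section 9.5 disclaims a statistical design, section 9.7 sets no pass/fail criterion, section 8.2 has no control group, and section 9.8 has no interim analysis. The visible text has no hypothesis test, threshold or pooled adequacy rate that would turn on how the two sources are combined.

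**4. How large the effect could be if a pooled rate were computed**

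Let *s* be the share of analysed participants with usable download data and *p* the share of those with an adequate result. Participants without data could all fail or all succeed:

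- lower bound = *s* × *p*
- upper bound = *s* × *p* + (1 − *s*)
- width = 1 − *s*, whatever *p* is

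The documents give neither *s* nor *p*. With *p* = 0.80 assumed, and counts based on 60, the lower end of the recruitment figure in section 7.3 ("Approximately 60-70 participants will be recruited for the trial by NTLSC"):

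| *s* (assumed) | Without data, of 60 | Lower bound | Upper bound | Width |
|---|---|---|---|---|
| 1.00 | 60 × 0.00 = 0 | 0.80 | 0.80 | 0 points |
| 0.90 | 60 × 0.10 = 6 | 0.90 × 0.80 = 0.72 | 0.72 + 0.10 = 0.82 | 10 points |
| 0.75 | 60 × 0.25 = 15 | 0.75 × 0.80 = 0.60 | 0.60 + 0.25 = 0.85 | 25 points |
| 0.50 | 60 × 0.50 = 30 | 0.50 × 0.80 = 0.40 | 0.40 + 0.50 = 0.90 | 50 points |

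This arithmetic is correct, but it says little about this trial. The width formula holds for any proportion with missing data. No visible text plans the rate, and a proportion judged adequate needs a cut-off, which the visible text does not give. The first row cannot be excluded, since section 8.8 enrols only people prescribed PAP.

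**5. Nights off the trial mask**

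Section 8.11 allows reversion. Section 9.10 says who is included, not that nights on another mask count as trial-mask data. Visit timing and any download window would be expected in section 8.10. Restricting results to trial-mask nights would need a record of which mask was worn each night. No visible section shows that such a record is kept, so the restriction might require new data and not just new wording.

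**The case for a change.** The best argument for a change is that having no formal test does not make a measure unimportant. The sponsor chose to place treatment adequacy among the primary outcomes, and even a descriptive result needs a source and a denominator. Hidden text might explain when a download applies, but it would not alter how the visible bullet mixes attributes and sources. A few words in sections 8.4.1, 8.4.2 and 9.10 would settle the matter.

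Part of this stands. The bullet would be clearer if it paired each attribute with its source, and the number of participants with PAP data should accompany any treatment or leak result. Pairing the sources is an optional clarification, and giving the number is ordinary reporting practice. Marking the data as conditional already tells the analyst that the results cover only those who have it. The argument does not show that a planned analysis would give a wrong answer, or that a decision would be made on opinion presented as physiology. The point about nights off the mask is possible but speculative while section 8.10 is unseen.

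**Conclusion.** The concern describes the wording correctly but does not call for a change. This is a gap that analysts fill sensibly: feedback is reported as feedback, PAP results are reported for participants who have them, and the number is given for both the treatment and the leak outcomes.

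No planned quantity in the visible text is affected. A whole-set adequacy rate, if someone chose to compute one, would be uncertain by exactly the share without downloads: anything from 0 points upwards, with 10, 25 or 50 points only under assumed shares of 90%, 75% or 50% with data.

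This conclusion rests on three assumptions: that the report keeps the two sources apart, that it states how many participants contributed PAP data, and that the redacted sections do not plan a pooled adequacy rate or a decision based on one. If the report claimed adequate treatment for the full section 9.10 set and counted opinion as evidence for those without downloads, the concern would apply to that claim.

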8.4.2. Secondary Outcomes

- Seal performance as measured by leak measurements/PAP data (if applicable).

[REDACTED]
 [REDACTED]

8.5. Variables

[REDACTED]	[REDACTED]	[REDACTED]

[REDACTED]	[REDACTED]
[REDACTED]	[REDACTED]

[REDACTED]	[REDACTED]	[REDACTED]

8.6. Measurements

8.7. Equipment

8.8. Inclusion / Exclusion criteria

Inclusion Criteria:

- Adult (22+ years of age)
- Able to give informed consent
- AHI ≥ 5 on diagnostic night
- Either prescribed APAP, CPAP or Bi-level PAP for OSA
- Fluent in spoken and written English

Exclusion Criteria:

[figure not shown]
- Inability to give informed consent
- Participant intolerant to PAP
- Anatomical or physiological conditions making PAP therapy inappropriate
- Current diagnosis of respiratory disease or CO₂ retention
- Pregnant or may think they are pregnant.

[REDACTED]	[REDACTED]
[REDACTED]	[REDACTED]

[figure not shown]
8.9. Point of Enrolment

Participants will be recruited; who are prescribed either APAP, CPAP or Bi-level PAP for OSA at NTLSC. The principal investigator (or those identified in the delegation log) will ask the subjects whether they are interested to take part in the trial. The participants who meet the inclusion/exclusion criteria and provide informed consent and will then be enrolled in to the trial. [REDACTED]

8.10. Participant Procedure

[figure not shown]

[REDACTED]	[REDACTED]
[REDACTED]	[REDACTED]

[figure not shown]

[REDACTED]	[REDACTED]

[REDACTED]	[REDACTED]
[REDACTED]	[REDACTED]
[REDACTED]	[REDACTED]

[REDACTED]	[REDACTED]	[REDACTED]
[REDACTED]	[REDACTED]	[REDACTED]
[REDACTED]	[REDACTED]	[REDACTED]

[REDACTED]	[REDACTED]	[REDACTED]
[REDACTED]	[REDACTED]	[REDACTED]

[REDACTED]	[REDACTED]	[REDACTED]
[REDACTED]	[REDACTED]	[REDACTED]

[REDACTED]	[REDACTED]
[REDACTED]	[REDACTED]
[REDACTED]	[REDACTED]

[REDACTED]

[REDACTED]

[REDACTED]

[REDACTED]

8.11. Withdrawal Criteria

Participants will be informed that they have the right to withdraw from the study at any time, without prejudice to their medical care, and are not obliged to state their reasons. The participants is informed that they can revert back to their usual therapy during the clinical investigation if they have reason to do so. Additionally the investigator may withdraw a participant at any time for the following reasons:

- Protocol Violation
- Safety concerns
- Serious illness
- Adverse event

[figure not shown]
The reason for participant discontinuation in the study is to be recorded in the CRF and source document.

[figure not shown]

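### Does letting participants go back to their usual therapy bias the leak, treatment and acceptability results in favour of the trial mask?

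*Combined protocol and SAP*

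**What the plan says.** Section 8.11 (Withdrawal Criteria) gives participants the right to withdraw at any time and says they "are not obliged to state their reasons". It adds that they "can revert back to their usual therapy during the clinical investigation if they have reason to do so". The same section requires a record when someone leaves: "The reason for participant discontinuation in the study is to be recorded in the CRF and source document".

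Section 9.10 (Selection Criteria) defines the analysis set: "All participants who consent, and are fitted with a mask that they attempt to sleep on will be included in the analysis". It refers the reader to section 8.10 for participant flow.

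The outcomes concerned are in section 8.4. Comfort is assessed "as measured by the custom questionnaires and recorded during the interviews". One primary outcome is that the mask "provides adequate treatment for OSA during in-home use, measured via participant feedback and PAP data download (if applicable"). Acceptability is obtained "through interview feedback/ participant questionnaire". The visible secondary outcome is "Seal performance as measured by leak measurements/PAP data (if applicable").

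Section 8.2 states that there is no control group, section 9.5 that no statistical design is needed, and section 9.7 that there is no pass/fail criterion because the aim is feedback. Section 9.6 sets a minimum of 30 participants on usability-testing grounds, and section 7.3 expects about 60 to 70 to be recruited.

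**The concern.** A participant may stop using the trial mask, stay in the study and remain in the analysis set. If the PAP device logs leak without identifying the mask (an assumption), the download mixes nights on two masks. People tend to revert for a reason. If the reason is a poor seal, their bad nights on the trial mask are diluted by better nights on the old one, and mean leak looks lower than it was.

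Acceptability has a parallel problem. Someone who leaves without explanation may give no rating, so the ratings could come mainly from people who liked the mask. With no control group, no comparator would expose the distortion. The study exists to find faults in the product, and the people who stop using the mask are likely to have met them. If mask use was not recorded as the study ran, it may be impossible to reconstruct.

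**Working it through.** The documents give no reversion rate, leak value or acceptance rate, so there is no figure of the plan's own to reproduce on this point. The rates and leak values below are assumptions. The exception is n = 60, the lower end of the recruitment range in section 7.3.

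**Leak, one unfavourable scenario.** Assume 20% of participants revert after 30% of their nights. Their leak is 30 L/min on the trial mask, and leak is 12 L/min on the usual mask and in everyone else.

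- Mean trial-mask leak: 0.8 × 12 + 0.2 × 30 = 15.6.
- Mean of a reverter's mixed download: 0.3 × 30 + 0.7 × 12 = 17.4.
- Blended mean over all participants: 0.8 × 12 + 0.2 × 17.4 = 13.08.
- Excess over 12: 3.6 true, 1.08 blended. Share hidden: 1 − 1.08/3.6 = 70%.

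The 70% is an input, not a finding. With r the share who revert, k the share of their nights on the trial mask, T their trial-mask leak and U the leak everywhere else, the true excess is r(T − U) and the blended excess is rk(T − U). The hidden share is 1 − k, here 1 − 0.3, whatever leak values are chosen.

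**Leak, direction.** If a share f of nights is on the usual mask, mean leak shifts by f × (usual-mask leak − trial-mask leak). With f = 0.2:

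| Usual minus trial leak | Shift in mean leak | Effect on trial mask |
|---|---|---|
| −10 | −2 | flattering |
| 0 | 0 | none |
| +10 | +2 | unfavourable |

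For f between 0.1 and 0.3, the same ±10 difference gives shifts of ±1 to ±3. A participant who reverts for comfort from a mask that seals well would move leak against the trial mask. Nothing in the documents settles the sign.

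**Acceptability.** Take n = 60 and about 80% acceptance among those who stay. Compare accepted/(n − reverters) with accepted/n, the second counting every reverter as not accepting.

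| Reverting | Reverters left out | Reverters counted as not accepting | Gap (points) |
|---|---|---|---|
| 5% (3) | 46/57 = 80.7% | 46/60 = 76.7% | 4.0 |
| 10% (6) | 43/54 = 79.6% | 43/60 = 71.7% | 8.0 |
| 20% (12) | 38/48 = 79.2% | 38/60 = 63.3% | 15.8 |
| 30% (18) | 34/42 = 81.0% | 34/60 = 56.7% | 24.3 |

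The left-hand figures arise only if reverters drop out of the denominator. Section 9.10 keeps them in the analysis set, and acceptability is asked directly, so a reverter still in the study can say that the mask was not acceptable. The gap is therefore an upper-end scenario that needs both missing feedback and a smaller denominator.

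**Where a handling rule would sit.** Section 2.5 (Data Management), 8.5 (Variables), 8.10 (Participant Procedure) and 8.12 (Number of Trial Subjects) are blacked out. No text is visible under 8.6 (Measurements) or 8.7 (Equipment). The participant and researcher questionnaires (Appendices B and C) are listed in the contents but not shown. Section 9.10 points to one of these places, 8.10, for participant flow.

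**AHI.** In the visible text it appears only as an inclusion criterion for the diagnostic night. The outcome is adequate treatment judged from feedback and the PAP download, so no claim about a biased AHI outcome can be tied to the text.

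**The case for a change.** The best argument for a change is that keeping a person in the analysis set neither creates a questionnaire answer nor removes usual-mask nights from a download. For PAP data, retention without a rule about nights is what would let the mixing in. The visible recording duty covers discontinuation, not reversion by someone who stays enrolled. Descriptive results are the study's only output, so the absence of a pass/fail rule does not make them unimportant. Recording a date of reversion would cost very little.

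Most of this stands as a description of the readable text: no visible sentence covers these nights or these people. It does not show that the plan is wrong. Whether mask use is recorded depends on procedures and forms that cannot be read. The permission to revert sits under the withdrawal heading and may describe people who are leaving, for whom a reason is to be recorded. The mechanism also needs one device to log both masks and a download that spans the switch, and neither can be checked.

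One possible remedy, counting everyone who leaves without explanation as not accepting in the main figure, is itself debatable. It would misclassify departures that have nothing to do with the mask and attach an outcome to a right the participant was given. It would be reasonable only as a sensitivity analysis.

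**Conclusion.** No change to the plan follows. The readable text leaves a handling rule unstated, but the places where it would be written are redacted or not visible, so its absence cannot be established. No stated rule or figure is shown to be wrong.

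The possible effect is real in principle but uncertain in both size and sign. Leak could move by about 1 to 3 units in either direction for a 10-unit difference between masks and 10% to 30% of nights on the usual mask. Acceptability could be overstated by about 4 to 24 points for 5% to 30% reversion at n = 60, and then only if reverters were left out contrary to section 9.10. All these rates are assumptions.

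The results are descriptive and feed design work, and no formal decision rests on a mean leak or an acceptance percentage. An analyst would ordinarily report how many participants reverted and any reasons given, over the section 9.10 set, and would summarise PAP data on trial-mask nights where these can be identified. That is ordinary reporting practice. It does depend on the unseen forms capturing the switch, which the public documents neither confirm nor contradict.
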